### 2.1.3. Exploratory Objectives

Exploratory study objectives are:

- To evaluate MMR at 3, 6, 9 and 18 months;
- To evaluate MMR at 12 months in patients with both Ph+ and Ph negative (-) CP CML;
- To evaluate molecular response (MR) and MR^2 at 3 and 6 months, respectively;
- To evaluate MR4.0 and MR4.5 at 3, 6, 9 and 12 months;
- To evaluate time to MMR, MR4.0, MR4.5 and CCyR;
- To evaluate the proportion of patients demonstrating a cumulative complete hematologic response (CHR) in patients with Ph+ and both Ph+ and Ph- CP CML;
- To estimate the time to transformation to accelerated phase (AP) and blast phase (BP) CML on treatment;
- To evaluate the type of BCR-ABL\* mutations present at treatment completion or discontinuation, or in case of suboptimal response, and

---

\* Fusion transcript or protein resulting from the 9;22 chromosomal translocation responsible for formation of the Philadelphia Chromosome

- To enable exploratory research through collection of banked biospecimen, unless prohibited by local regulations or ethics committee (EC) decision.

## 2.2. Study Design

This is a phase 2, open-label, single-arm study designed to evaluate efficacy and safety of bosutinib alone in Japanese adult patients with newly diagnosed CP CML. Patients will receive bosutinib treatment at a starting dose of 400 mg once daily (QD). The dose of bosutinib is allowed to be escalated (up to a maximum of 600 mg QD) for unsatisfactory response or reduced for toxicity.

This study has approximately 52 weeks of planned patient accrual. Each patient will have 12 months (48 weeks) of Core Treatment Phase and the following  $\geq 24$  months (96 weeks) of Extension Phase. After treatment discontinuation, the patient enters Long-Term Follow-Up. The Extension Phase or Long-Term Follow-Up will continue until the end of the study.

The study will be open for enrollment until approximately 60 Ph+ CML patients with b2a2 and/or b3a2 transcripts have been registered. Bone marrow aspirate to assess the Ph status will be obtained at screening, patients with known Ph- prior to registration are not eligible for this study. However, as confirmation of the Ph status prior to registration is not mandatory, Ph- CML patients may also be included. Approximately 3 Ph- CML patients are expected to be registered as approximately 5% of the patients with BCR-ABL-positive CML are diagnosed as Ph- CML. All patients will be treated and/or followed up to approximately 3 years (144 weeks) after registration of the last patient, or until study termination, whichever comes first. Patients who permanently discontinue study treatment will be followed for survival, investigator-assessed transformation to AP/BP, duration of response and disease progression, and initiation/response to further anti-cancer therapies, including stem cell transplantation (where applicable).

## 3. ENDPOINTS AND BASELINE VARIABLES: DEFINITIONS AND CONVENTIONS

### 3.1. Primary Endpoint

#### 3.1.1. MMR at 12 Months

The primary endpoint is the MMR at 12 months (48 weeks). All Ph+ CP CML patients harboring b2a2 and/or b3a2 transcripts will be assessed and follow-up for the MMR as the primary endpoint.

The MMR is defined as  $\leq 0.1\%$  BCR-ABL on the international scale (IS) by quantitative reverse transcriptase polymerase chain reaction (RT-qPCR). See [Appendix 1.1](#) for the details.

### 3.2. Secondary Endpoints

#### 3.2.1. MMR by 12 and 18 Months

The MMR by 12-month and 18-month visit will be assessed.

### 3.2.2. CCyR

The CCyR by 12-month visit will be assessed.

The CCyR is defined as absence of detectable Ph. See [Appendix 1.2](#) for the details.

### 3.2.3. Duration of MMR and CCyR

The duration of response (MMR and CCyR, respectively) is measured from the first date of response until the first date of confirmed loss of response, treatment discontinuation due to progressive disease (PD), or death due to PD within 28 days after last dose. A loss of response must be confirmed by a second consecutive loss at least 4 weeks later, treatment discontinuation due to PD or death due to PD within 28 days of last dose. A PD is defined as investigator assessed progression reported on the case report form (CRF). Treatment discontinuation due to PD or death due to PD within 28 days of last dose without loss of response will be considered a confirmed loss. An unconfirmed loss followed by treatment discontinuation due to suboptimal response is considered a confirmed loss.

For loss of MMR, the loss must be at least 5 times the smallest recorded ratio. Loss of CCyR is defined as at least one Ph+ metaphase.

Duration of response will be counted while a patient is on treatment. If treatment ceases and loss of response has not occurred, the patient will be censored at the last valid assessment on treatment for the respective endpoint.

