6.5. Patient Withdrawal

Patients may withdraw from treatment at any time at their own request, or they may be withdrawn at any time at the discretion of the investigator or sponsor for safety (see also the Section 8.1.3), behavioral reasons, or the inability of the patient to comply with the protocol-required schedule of study visits or procedures at a given study site.

Reasons for withdrawal of study treatment may include:

- Treatment failure (meeting 1 or more of the following definitions);
 - Transformation to AP or BP at any time (disease progression).
 - After dose escalation (as specified in Section 5.4.1), or documented AEs prohibiting dose escalation and if 1 of the following conditions is met:
 - Failure to achieve a CHR after a minimum of 24 weeks on treatment.
 - Failure to achieve at least a minimal cytogenetic response after a minimum of 24 weeks on treatment.
 - Failure to achieve a major cytogenetic response (MCyR) after a minimum of 48 weeks on treatment.
 - Failure to achieve a CCyR after a minimum of 72 weeks on treatment.
 - Loss of MCyR or CCyR (need at least 30% increase for MCyR or at least one Ph+ metaphase for CCyR confirmed by a follow-up cytogenetic analysis ≥ 4 weeks later).
 - Loss of CHR. Loss of CHR is defined as the appearance of any of the following, confirmed by a second determination ≥ 4 weeks later (unless associated with CML-related treatment discontinuation):
 - ✓ White blood cell count (WBC) that rises to $>20.0 \times 10^9/L$.
 - ✓ Platelet count that rises to $\geq 600 \times 10^9/L$.

- ✓ Appearance of palpable spleen or other extramedullary involvement proven by biopsy.
- ✓ Appearance of 5% myelocytes in the peripheral blood.
- ✓ Appearance of blasts or promyelocytes in the peripheral blood.
- For patients not achieving a CHR: doubling of WBC at least 1 month apart with the second value $>20 \times 10^9/L$ and maintained in subsequent assessments for at least 2 weeks.
- Global deterioration of health status requiring discontinuation;
- Unacceptable toxicity;
 - Dose is held for longer than 4 weeks for treatment-related toxicity (without consultation with sponsor). Of note, in some instances, if the investigator and sponsor determine it is appropriate, a patient may be allowed to continue on treatment if recovery takes longer than 4 weeks.

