7.1.1.2. Mutation Analysis

Correlation of mutations with treatment response will be studied. The blood samples collected for RT-qPCR will also be used for mutation analysis and will be drawn every 3 months (every 12 weeks) up to years 2 (Core Treatment Phase and Extension Phase) and then every 6 months (every 24 weeks) (Extension Phase). No mutation analysis will occur at Screening. Mutation analysis will be performed in case of either lack of response, suboptimal response or loss of response defined as: failure to achieve MMR at 12 months; loss of MMR AND rise in BCR-ABL transcript level by ≥ 5 -fold from the lowest value achieved during the study; at the End of Treatment/Withdrawal visit. For patients with a positive mutation identified during therapy, follow-up mutation analyses will be performed in subsequent samples. For a patient with a negative mutation result immediately following relapse, continued mutation analyses may be performed at a frequency of every 6 months (every 24 weeks) as needed.

Further mutation analyses will be performed retrospectively as appropriate on patient samples if mutations are identified. Alternative methodologies with improved mutation detection sensitivity may be used for identifying mutations in earlier samples.

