9.2.2.3. Duration of Response

The analysis of secondary endpoints relating to duration of response, such as duration of MMR and CCyR will be based on the estimations of the quartiles of duration and yearly rates using the Kaplan-Meier method. For the analysis of CCyR, the proportion of patients who have confirmed loss of response will also be evaluated.

The duration is measured from the first date of response until the first date of confirmed loss of response, treatment discontinuation due to progressive disease, or death due to disease

progression within 28 days after last dose. An unconfirmed loss followed by treatment discontinuation due to suboptimal response is considered a confirmed loss. Duration of response will be counted while a patient is on treatment and 28 days after last dose. If loss of response has not occurred, the patient will be censored at the last valid assessment.

The duration of MMR will be analyzed for the modified as-treated population and as-treated population separately. The duration of CCyR will be calculated using the modified as-treated population.

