9.2.2.4. Event-Free Survival and Overall Survival

The analysis of EFS and OS will be similar to that for duration of response just described.

EFS was defined as the time from first dose to the occurrence of the earliest of the following events while on treatment:

- Death due to any cause.
- Transformation to AP or BP (on treatment).
- Loss of CHR.
 - Loss of CHR is defined as the appearance of any of the following, confirmed by a second determination ≥ 4 weeks later (unless associated with CML-related treatment discontinuation):
 - ✓ WBC count that rises to $>20.0 \times 10^9/L$.
 - ✓ Platelet count that rises to $\geq 600 \times 10^9/L$.
 - ✓ Appearance of palpable spleen or other extramedullary involvement proven by biopsy.
 - ✓ Appearance of 5% myelocytes in the peripheral blood.
 - ✓ Appearance of blasts or promyelocytes in the peripheral blood.
- Loss of CCyR.
 - ✓ Loss of CCyR is defined as at least one Ph+ metaphase confirmed by a second determination ≥ 4 weeks later (unless associated with CML-related treatment discontinuation).
- For patients not achieving a CHR: doubling of WBC at least 1 month apart with the second value $>20 \times 10^9/L$ and maintained in subsequent assessments for at least 2 weeks.

OS is defined as the time from first dose to death due to any cause.

The EFS will be calculated using the modified as-treated population. OS will be analyzed in the modified as-treated population and as-treated population separately.

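### Duration of response and event-free survival treat an unconfirmed loss differently when treatment stops, so a few losses may be censored in the drug's favour

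*SAP*

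**What the plan says.** SAP 3.2.3 sets the confirmation rule for duration of response: "A loss of response must be confirmed by a second consecutive loss at least 4 weeks later, treatment discontinuation due to PD or death due" (the sentence goes on to limit such deaths to progressive disease, no more than 28 days past the final dose). One further route follows: "An unconfirmed loss followed by treatment discontinuation due to suboptimal response is considered a confirmed loss". Protocol 9.2.2.3 carries the same sentence. PD is broad here: "A PD is defined as investigator assessed progression reported on the case report form (CRF").

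The default for everyone else is censoring: "If treatment ceases and loss of response has not occurred, the patient will be censored at the last valid assessment on treatment". The protocol's window is longer: "Duration of response will be counted while a patient is on treatment and 28 days after last dose".

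Protocol 6.5 gives reasons why study treatment may be withdrawn. The first is "Treatment failure (meeting 1 or more of the following definitions"). Its definitions are transformation to AP or BP (labelled disease progression), missed response milestones, confirmed loss of MCyR or CCyR, loss of CHR, and a WBC criterion for patients without CHR. Suboptimal response is not on the list, and neither is loss of MMR.

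For EFS, protocol 9.2.2.4 requires a second determination of CCyR loss at least 4 weeks later, "unless associated with CML-related treatment discontinuation". SAP 3.2.4 item 4 keeps that exception but drops the confirmation clause in front of it, and refers back to 3.2.3 for the definition of loss.

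**The concern.** Two secondary endpoints rest on the same event, loss of CCyR, but use different rules for a loss that was never confirmed because treatment stopped. The EFS exception covers every CML-related stop. The duration rule covers PD and a term that neither document defines as a discontinuation reason.

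A patient with one unconfirmed loss who stops for a treatment failure recorded under neither label falls to the censoring rule. The censoring date can be the very assessment that showed the loss. Such censoring would be informative, since the stop is itself caused by the disease. It would lengthen the estimated duration of response and lower the proportion with confirmed loss that SAP 6.2.2 and 6.2.3 also report. If the term is left undefined, event status would be settled at programming, in an open-label study with outcomes already visible.

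**Working it through.** Neither document states a figure for duration of response, so there is none to reproduce. The check compares the rules and then illustrates the size.

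**Step 1. One unconfirmed loss, by what happens next**

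| What follows | Duration of response | Protocol EFS (CCyR loss only) |
|---|---|---|
| Second loss at least 4 weeks later, inside the window | Event | Event |
| Stop for PD as reported on the CRF | Event | Event |
| PD death within 28 days of last dose | Event | Event (death) |
| Stop for suboptimal response | Event | Event, if regarded as CML-related |
| Stop for treatment failure recorded as neither PD nor suboptimal response | No rule makes it an event; read literally, censored | Event |

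Only the last row differs.

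**Step 2. Who can reach the last row**

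- Treatment failure by CCyR loss does not normally lead there. Protocol 6.5 requires a follow-up cytogenetic analysis at least 4 weeks later, and 7.1.1 repeats this. Such a loss is already confirmed.
- A patient withdrawn for loss of CHR can reach it with a single unconfirmed CCyR or MMR loss. Protocol 6.5 waives confirmation of the CHR loss itself when the stop is CML-related.
- A patient whose failure is declared before the confirmatory sample can reach it. The Schedule of Activities and protocol 7.1.1 require an end-of-treatment marrow only if the previous one was more than 12 weeks earlier, so a second marrow need not exist.
- For MMR, protocol 7.1.1.1 calls for a repeat sample within 4 to 6 weeks of a loss with a rise of at least 5-fold. The gap arises only if treatment stops before that sample counts.

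The window adds to this. The End of Treatment visit falls 7 to 28 days after the last dose (protocol 6.4). If dosing went on for a while after the loss sample, that visit can supply a second sample at least 4 weeks later. The protocol's window would count it; the SAP's on-treatment wording may not.

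**Step 3. Size per patient (illustration)**

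Inputs from the documents: 60 patients; 77% CCyR by 12 months and 47% MMR at 12 months on bosutinib in the Phase 3 study AV001 (protocol 1.2.4). Responders R: 0.77 × 60 = 46.2, taken as 46; 0.47 × 60 = 28.2, taken as 28.

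Assumptions: L = 3 or 5 losses, k of them censored instead of counted, the censored ones first in time, no other censoring. After k censorings, R − k patients are at risk and L − k events follow, so the Kaplan-Meier proportion still in response is

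S = (R − L) / (R − k).

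| Endpoint | L | k = 0 | k = 1 | k = 2 |
|---|---|---|---|---|
| CCyR, R = 46 | 3 | 43/46 = 93.5% | 43/45 = 95.6% | 43/44 = 97.7% |
| CCyR, R = 46 | 5 | 41/46 = 89.1% | 41/45 = 91.1% | 41/44 = 93.2% |
| MMR, R = 28 | 3 | 25/28 = 89.3% | 25/27 = 92.6% | 25/26 = 96.2% |
| MMR, R = 28 | 5 | 23/28 = 82.1% | 23/27 = 85.2% | 23/26 = 88.5% |

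Each censored loss adds about 2 points for CCyR and 3 to 4 points for MMR. If the censored losses came last in time, S = (R − L + k)/R and the step is 1/46 = 2.2 or 1/28 = 3.6 points, so the order hardly matters. The crude proportion with confirmed loss moves by the same 1/R. More patients may reach MMR at some time than are in MMR at month 12, and a larger R would make the MMR step smaller.

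**The case against.** The strongest reply is that *suboptimal response* may already cover these patients. The list in protocol 6.5 gives reasons that may apply and is not closed, and the CRF categories are not in the documents, so this may simply be the CRF label. Protocol 7.1.1.2 groups "lack of response, suboptimal response or loss of response" under one shared definition that includes loss of MMR. Protocol 5.4.2 speaks of escalation for suboptimal response as set out in 5.4.1, and 5.4.1 includes loss of hematologic, cytogenetic or molecular response. This stands as a possible reading; it does not replace a definition. If it is the intended one, writing it down costs nothing.

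Second, PD is whatever progression the investigator reports on the CRF, so it is not limited to AP or BP, and some failures will count by that route. This also stands, and it narrows the gap.

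Third, the SAP's on-treatment wording might include 28 days, since SAP 6.2.4 points to 6.3.5, where transformation is counted up to 28 days after the last dose. SAP 3.2.3 makes no such reference, so the window needs stating there.

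A reader might infer more: that every loss followed by withdrawal for treatment failure is censored as still in response. The documents do not support this, because failure by CCyR loss already requires the confirming analysis. A reader might also apply the 4% treatment failure on bosutinib in the earlier Phase 3 study (protocol 1.2.3) to get 0.04 × 60 = 2.4 affected patients. That does not follow. The protocol does not give that study's definition of failure. Under this protocol's definition, failure also includes transformation, which can count as PD, and patients who never responded, who cannot enter the analysis.

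**Conclusion.** The mismatch between the two rules is real, and on a literal reading one CCyR loss can be an EFS event under the protocol and censored in duration of CCyR. For MMR the gap is within the duration rule only; there is no EFS contrast. It is not established that duration will be overstated: that depends on whether any patient stops with an unconfirmed loss for a failure recorded as neither PD nor suboptimal response. The number may be zero.

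If such patients occur, the error always favours the drug, by about 2 points (CCyR) or 3 to 4 points (MMR) each under the assumed responder numbers. With few losses expected, one patient is visible in the result. Duration of response is a descriptive secondary endpoint with no test (SAP 5.1), and the primary analysis is unaffected. The point justifies a small text change.

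**What to change.** 1. In SAP 3.2.3, and in protocol 9.2.2.3 to match, replace discontinuation due to suboptimal response with CML-related treatment discontinuation, the EFS term. List which CRF discontinuation reasons it covers before database release.
2. State that the loss is dated at the first loss assessment.
3. In SAP 3.2.4 item 4, restore the protocol's requirement of a second determination at least 4 weeks later ahead of the exception. As it stands, the bare exception can be read as excluding losses linked to a CML-related stop, the opposite of the protocol's rule.
4. Give SAP 3.2.3 the protocol's window of 28 days after the last dose, so that a confirming End of Treatment sample counts.

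The cost is a few phrases and one mapping of reasons already collected. Protocol section 9 and SAP section 2 let the SAP modify analyses other than the primary without an amendment, so the SAP can change first. Duration is reported at both the primary and the final analysis (SAP 7.2.2 and 7.2.3), so one change serves both. The downside is that a few unconfirmed losses will count, and duration will look slightly less favourable.

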### 3.2.4. EFS

The EFS is measured from the date of first dose until the first occurrence of one the following events, censored at the earlier of the last valid hematologic or cytogenetic assessment for those without events:

1. Death due to any cause;
2. Transformation to AP or BP (on treatment; see [Appendix 1.3](#));
3. Loss of CHR.
  - Loss of CHR is defined as the appearance of any of the following, confirmed by a second determination  $\geq 4$  weeks later (unless associated with CML-related treatment discontinuation):
    - WBC count that rises to  $>20.0 \times 10^9/L$ ;
    - Pplatelet count that rises to  $\geq 600 \times 10^9/L$ ;
    - Appearance of palpable spleen or other extramedullary involvement proven by biopsy;
    - Appearance of 5% myelocytes in the peripheral blood, or

- Appearance of blasts or promyelocytes in the peripheral blood.
4. Loss of CCyR (unless associated with CML-related treatment discontinuation; refer to [Section 3.2.3](#) for the definition of loss of CCyR), or
  5. For patients not achieving a CHR: doubling of white blood cell (WBC) at least 1 month apart with the second value  $>20 \times 10^9/L$  and maintained in subsequent assessments for at least 2 weeks.

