- j. ECHO or MUGA to be performed at screening (within 2 weeks prior to registration) and at End of Treatment/Withdrawal or at Week 96, whichever is earlier. If a patient has undergone ECHO or MUGA as standard of care prior to entering the study, the procedures will not have to be repeated if results are available and the procedures were performed within 28 days prior to registration. To enable meaningful clinical comparison, every effort must be made to ensure that the imaging method used to assess cardiac function remains consistent for each individual patient through the course of the trial.

- k. Hematology including automated complete blood count (CBC) (eg, hemoglobin, RBC, WBC, platelets and hematocrit) with differential counts (eg, neutrophils, lymphocytes, monocytes, eosinophils, basophils, metamyelocytes, myelocytes, promyelocytes, myeloblasts, unspecified blast cells and band cells) to be performed locally. Hematology assessments are to be performed at Screening, Weeks 1, 2, 3, 4, 6, 8, 10, 12, 16, 20, 24 and then every 12 weeks for the next 72 weeks (ie, until the end of Year 2), then every 24 weeks, and End of Treatment/Withdrawal visit. CHR must be confirmed by 2 assessments at least 4 weeks apart. Hematology to be repeated at least 4 weeks after achieving first CHR.
- l. Chemistry panel to be performed locally including: sodium, potassium, chloride, carbon dioxide or bicarbonate (if available), blood urea nitrogen (BUN) or urea, creatinine, glucose, total protein, albumin, calcium, alkaline phosphatase, amylase, lipase, phosphorous or phosphate, and magnesium. Creatine kinase (CK) also to be performed locally. Abnormally high CK values should be confirmed and fractionated (where possible). Uric acid to be obtained until patient achieves a CHR. Supplementation is advised for potassium levels or magnesium levels below the lower limit of normal (LLN), with consideration of the patient's underlying renal function.
- m. Liver Function tests to be performed locally including: total bilirubin, aspartate aminotransferase (AST) and alanine aminotransferase (ALT).
- n. Coagulation panel to be performed locally including: prothrombin time (PT) expressed as either PT or international normalized ratio (INR) and partial/activated partial thromboplastin time (PTT or aPTT).
- o. The first dose of study drug should occur no later than 3 business days after registration of the patient, with the day of first study drug administration = Day 1.

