- p. Bone marrow obtained as part of standard of care prior to signing informed consent document can be used at screening as long as it was collected within 28 days prior to registration. **Once CCyR or MMR has been achieved, bone marrow aspirates will be performed only if clinically indicated (eg, suboptimal response, suspect disease progression or failed/inadequate Week 48 assessment).** Patients completing treatment for cytogenetically confirmed treatment failure do not need to repeat bone marrow at treatment completion. Patients ending treatment for reasons other than cytogenetically confirmed treatment failure must undergo treatment completion bone marrow aspirate if previous bone marrow aspirate performed >12 weeks prior. If loss of major molecular response occurs in combination with a $5 \times$ PCR increase for BCR-ABL, a bone marrow aspirate for chromosome banding analysis (CBA) should be obtained.
- q. Cytogenetics analysis must be performed so that dose-escalation rules can be appropriately applied (eg, patient should not have 12-week bone marrow aspirate before Day 84 so that at least 12 weeks from first dose is assessed). Cytogenetic assessment of bone marrow aspirate will be performed locally. If cytogenetics is used, it must be performed by CBA of marrow cell metaphases, counting at least 20 metaphases, at 12, 24, 36, and 48 weeks, until CCyR or MMR is achieved, then every 48 weeks.
- r. Local PCR result for BCR-ABL confirmation is acceptable prior to informed consent where this has already been conducted as part of initial diagnosis of a patient, provided this molecular diagnosis of CP CML has been made ≤ 6 months prior to registration. However, central PCR sample must always be conducted after informed consent, as this is a study-specific procedure.

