#### **5.3.2. Cytogenetic Response Assessment**

Handling of missing bone marrow data will take the following steps:

1. If bone marrow cytogenetics results are not available and a MMR is achieved on a specific date, then a CCyR response will be imputed for that date.
2. If bone marrow cytogenetics results are available where <20 metaphases analyzed with zero Ph+ cells and a MMR is achieved on a specific date, then a CCyR response will be imputed for that date.

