#### **5.3.4. Time-to-Event Data**

The primary missing data handling method will be censoring. A patient withdrawing from the study without experiencing the event of interest will be censored at the last valid (ie, evaluable) assessment of that event. A patient who fails on treatment, after missing two or more assessments of both hematologic and cytogenetic response, will be censored for on-treatment EFS at the last hematologic or cytogenetic assessment. A patient, who dies after treatment discontinuation during long-term follow-up and after missing two or more long-term follow-up assessments, will be censored for off-treatment EFS at the last assessment at which the patient was found to be alive and event-free. See also [Section 3.2.3](#) for duration of MMR or CCyR.

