#### **6.2.4. EFS**

EFS will be analyzed using the cumulative incidence method adjusting for the competing risk of treatment discontinuation without the event, and yearly rates and percentiles will be displayed. This will be indicated as the on-treatment EFS. As a definition of “on-treatment” is described in [Section 6.3.5](#), the transformation to AP and BP on treatment will be considered as an event in the analysis of EFS. This means that if the first transformation to AP and BP is occurred after 28 days from the last dose, this will not be considered as an event in the analysis of EFS.

As a reference, the EFS using the transformation to AP and BP occurred after 28 days from the last dose instead of the transformation to AP and BP on treatment will also be assessed using the same analysis method. This will be indicated as the off-treatment EFS.

The on-treatment EFS and off-treatment EFS will be analyzed in the modified as-treated population.

The off-treatment EFS will only be evaluated at the FA (refer to [Section 7.2.3](#) with respect to the FA).

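### SAP 3.2.4 censors event-free patients for EFS at the earlier of two assessment dates, which discards follow-up in responders still on treatment and overstates EFS event incidence

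*SAP*

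**What the plan says.** **EFS censoring (SAP 3.2.4).** Patients without an event are "censored at the earlier of the last valid hematologic or cytogenetic assessment for those without events".

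**Estimator (SAP 6.2.4).** Cumulative incidence, "adjusting for the competing risk of treatment discontinuation without the event", reported as yearly rates and percentiles. On-treatment EFS is due at both the primary and the final analysis (SAP 7.2.2, 7.2.3). Only off-treatment EFS waits for the final analysis.

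**Hematology (Schedule of Activities, footnote k).** After Week 24, "then every 12 weeks for the next 72 weeks (ie, until the end of Year 2), then every 24 weeks", whatever the response.

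**Marrow (Schedule of Activities, footnotes p and q).**
- Footnote p: "Once CCyR or MMR has been achieved, bone marrow aspirates will be performed only if clinically indicated".
- Footnote q: cytogenetics at 12, 24, 36 and 48 weeks, "until CCyR or MMR is achieved, then every 48 weeks". The marrow row is also marked in the Extension Phase column.
- Footnote p again: patients ending treatment for reasons other than cytogenetically confirmed failure "must undergo treatment completion bone marrow aspirate if previous bone marrow aspirate performed >12 weeks prior".

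**Imputation (SAP 5.3.2).** Where marrow "results are not available and a MMR is achieved on a specific date, then a CCyR response will be imputed" for that date. Neither this section nor 3.2.4 says whether such a value is a valid cytogenetic assessment.

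**Neighbouring rules.** Protocol 9.2.2.4 refers EFS back to 9.2.2.3, which censors at the last valid assessment. SAP 6.3.5 censors time to transformation, itself an EFS component, at the last valid hematologic assessment. Neither takes the earlier of two dates.

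**The concern.** Because hematology is at least as frequent as marrow and usually more so, the last marrow date normally decides the censoring time of an event-free patient. Take two responders whose last marrow was at Week 24. One is event-free on bosutinib with hematology at Week 96. That patient is censored at Week 24, and 96 - 24 = 72 weeks of observed event-free time are dropped. The other loses CHR or stops treatment shortly before Week 96 and is kept in the risk set to that date.

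Follow-up is therefore shortened according to outcome. Protocol 5.4.1 adds to this: marrow cytogenetics are to be resumed on loss of MMR with a five-fold PCR rise, so patients who are getting worse acquire later marrow dates than stable ones. Later risk sets are tilted towards patients who go on to fail or stop. Both the EFS event incidence and the competing discontinuation incidence then come out too high, which is against the drug. At stake are the yearly EFS rates and percentiles in the primary and final reports.

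**Working it through.** The documents give no EFS rate or event count, so there is no plan figure to reproduce. The check asks how far the rule moves the estimate under each reading.

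**Inputs from the documents.** Accrual 52 weeks. Follow-up at the cut-off is at least 48 weeks (primary analysis) or 144 weeks (final analysis) from last registration. Hematology, PCR and marrow follow the Schedule of Activities. CCyR by 12 months is 77% (AV001, Protocol 1.2.4).

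**Assumptions not in the documents.** Event hazard 2% or 4% per year; discontinuation hazard 10% or 20% per year; a 48-week year; cumulative response 40/60/70/77% at Weeks 12/24/36/48.

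**True value.** With event hazard a and discontinuation hazard b, incidence at year k is F(k) = a/(a+b) × [1 - exp(-(a+b)k)]. For 2% and 10% at year 3: 0.02/0.12 × (1 - exp(-0.36)) = 5.0%.

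**Estimator.** Aalen-Johansen: the sum over event times of S(t-) × d/n. Early censoring of event-free patients shrinks n, while every d is kept. There were 300,000 simulated patients per setting. Only event-free patients on treatment are censored.

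**Final analysis, Week 144 incidence (%)**

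| Event / discontinuation per year | True | Last hematologic | Earlier, fn p | Earlier, fn q | Earlier, MMR-imputed | Earlier, completion marrow |
|---|---|---|---|---|---|---|
| 2% / 10% | 5.0 | 5.1 | 9.7 | 5.3 | 5.1 | 5.1 |
| 2% / 20% | 4.4 | 4.4 | 6.7 | 4.6 | 4.4 | 4.4 |
| 4% / 10% | 9.8 | 9.9 | 17.8 | 10.3 | 9.9 | 9.9 |
| 4% / 20% | 8.6 | 8.6 | 12.5 | 8.9 | 8.6 | 8.6 |

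Footnote p against last hematologic: 9.7/5.1 = 1.90, 6.7/4.4 = 1.52, 17.8/9.9 = 1.80, 12.5/8.6 = 1.45. Under footnote p, 23-28 of 60 are at risk beyond Week 48 instead of 47-53, and 3-4 beyond Week 144 instead of 17-23. With response of 66% or 79% by Week 48 (2% / 10%), footnote p gives 8.4% or 10.1%, against 5.1%.

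The MMR-imputed column credits every responder with a current MMR, which is the favourable limit. A smaller simulation (60 patients, 4,000 runs, no marrow after response) that credited 50-70% of responders gave inflation of about 10-30%.

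**Primary analysis, Week 48 / Week 96 incidence (%)**

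| Event / discontinuation per year | True | Last hematologic | Earlier, fn p | Earlier, fn q | Earlier, MMR-imputed |
|---|---|---|---|---|---|
| 2% / 10% | 1.9 / 3.6 | 1.9 / 4.4 | 3.4 / 13.9 | 2.2 / 8.6 | 1.9 / 4.7 |
| 2% / 20% | 1.8 / 3.2 | 1.8 / 3.8 | 2.9 / 8.3 | 2.0 / 6.4 | 1.8 / 4.0 |
| 4% / 10% | 3.7 / 7.0 | 3.7 / 8.5 | 6.5 / 24.8 | 4.2 / 16.0 | 3.7 / 9.1 |
| 4% / 20% | 3.6 / 6.4 | 3.6 / 7.7 | 5.6 / 15.6 | 4.0 / 12.4 | 3.6 / 8.1 |

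Beyond Week 48, 37-41 of 60 are at risk with last-hematologic censoring, 24-26 under footnote q and 4-6 under footnote p. The longest possible follow-up here is 52 + 48 = 100 weeks, so Week 96 lies at the edge of the data. Even last-hematologic censoring overshoots there (3.8-8.5% against a true 3.2-7.0%), because event-free patients fall back to their last visit. The comparison between rules is the informative one.

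**The case against.** A reader might infer that marrows stop by design after response, so that responders all leave the EFS risk set in year 1. The documents do not support this. It rests on one sentence of footnote p. Footnote q keeps cytogenetics every 48 weeks, the Extension Phase column is marked for marrow, and footnote p itself asks for a completion marrow. Responders who later have an event or discontinue are not removed early on any reading.

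A reader might also infer that patients in CCyR without MMR are lost on every reading. They are not rescued by imputation, but the 48-weekly marrow and the completion marrow apply to them as well.

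Nor does SAP 5.3.4 plainly contradict 3.2.4. Its sentence that a patient "will be censored for on-treatment EFS at the last hematologic or cytogenetic assessment" covers a different group: those who fail after missing two or more assessments of both kinds.

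Finally, the earlier date has a rationale, since only up to then is every EFS component known to be absent. EFS is also descriptive: SAP 5.1 tests nothing but the primary endpoint, and the bias runs against the drug.

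Most of this stands and limits the size. It does not rescue the rule. The stricter standard is applied only to patients without an event. At the primary analysis ongoing patients have had no completion marrow, so that remedy is not available. And a rate that depends on which footnote the programmer follows is not prespecified.

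**Conclusion.** The rule in SAP 3.2.4 is wrong as written. It makes censoring depend on doing well and overstates EFS event incidence.

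- **Final analysis.** About 1.4 to 1.9 times too high at 3 years if footnote p alone applies and imputed CCyR earns no credit. Small or nil under footnote q, with a completion marrow for all, or with MMR-imputed CCyR counted as valid. Partial imputation credit lies in between.
- **Primary analysis.** Under footnote q, Week 48 is slightly high (2.0-4.2% against 1.8-3.7%), and Week 96 is 6.4-16.0% against 3.8-8.5% with last-hematologic censoring. Footnote p is worse at both times.

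The hazards and the timing of response are assumed. The figures show mechanism, direction and range, and do not predict results. The primary endpoint and its test are unaffected.

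**What to change.** 1. In SAP 3.2.4, censor event-free patients at the later of the last valid hematologic or cytogenetic assessment on treatment (up to 28 days after last dose).
2. Keep the SAP 5.3.4 rule for failures after two or more missed assessments, and word it consistently with 3.2.4.
3. State whether a CCyR imputed from MMR under SAP 5.3.2 is a valid cytogenetic assessment.
4. Reconcile footnotes p and q on marrow after response. Which schedule applies is for the sponsor to settle.

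**Cost.** Items 1 to 3 are SAP wording and need no new data. Item 4 is a clarification of the protocol's schedule. The downside of item 1 is that a loss of CCyR not yet detected between marrows counts as event-free time, although hematology and PCR monitoring continue. Since the correction lowers the reported event rate, it should be made before EFS data are examined.
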